### 6.2 SECONDARY HYPOTHESES

Neurologically intact adults with SCD will have significantly lower scores on other neuropsychological tests of executive function when compared to adult controls.

A larger percentage of adult patients with abnormal MRIs will have abnormal NP testing than those with normal MRIs.

Volumetric MRI will detect brain dysfunction in patients with abnormal neurocognitive tests but normal qualitative MRI.

Correction of anemia with transfusion therapy will improve the cognitive function in SCD patients with abnormal neurocognitive testing more than standard care.

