#### Summary of Volumetric Outcome Measures

The following results (reported as volumes) will be delivered:

- Total Intracranial Volume (ICV)
- Left and Right Hippocampus
- Cortical Gray Matter
- White Matter
- White Matter Lesions
- Cortical & Subcortical Lacunae
- Sulcal CSF
- Ventricular CSF

### 10.3 VISIT 3

Visit 3 must occur within four weeks of Visit 2. At Visit 3, the study component that was not conducted at Visit 2 will be completed. For example, if the Neuropsychological Battery was completed at Visit 2, then the MRI will be completed at Visit 3. If the MRI was completed at Visit 2, then the NP Battery will be completed at Visit 3.

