## 13.2 STATISTICAL METHODS

The primary clinical hypothesis is that the mean score for adult patients with SCD on the WAIS-III PIQ scale will be at least one standard deviation below the mean score of a group of community controls matched for site, age, and education. We expect the adult patients with SCD will have a mean WAIS-III PIQ of 85 or less and the community control group will have a mean of 100. Although the primary hypothesis expresses the expected direction of effect, the statistical analysis will follow common practice and use a 2-sided hypothesis test with an alpha of 0.05.

To test the primary hypothesis, we will use a GLM to model the data. At each site participating in this study we will match the patients using a ratio of 3 patients to 1 community controls, but if necessary we will still statistically control for site, age, sex, and education. Model selection techniques will be used to determine the most parsimonious models. For statistical analysis we express the primary hypothesis, adult SCD patients will have an adjusted mean WAIS-III PIQ different from the community based control group adjusted mean WAIS-III PIQ (based on the final model):

$$H_0: \text{Adj\_}\mu_{\text{SCD}} - \text{Adj\_}\mu_{\text{control}} = 0$$

$$H_a: \text{Adj\_}\mu_{\text{SCD}} - \text{Adj\_}\mu_{\text{control}} \neq 0.$$

The first secondary hypothesis is the same as the primary hypothesis with other NP tests being used as the response; therefore, the analysis for these hypotheses will be the same as the primary hypothesis.

The 2nd secondary hypothesis is that patients with SCD and abnormal MRIs will have a higher proportion of abnormal NP test results than the patients with SCD and normal MRIs. The statistical analysis of this hypothesis will follow common practice and use a 2-sided hypothesis test with an alpha of 0.05. For statistical analysis we express this secondary hypothesis as:

Cortical gray matter volume, hippocampal volume, white matter lesions (WML), cortical strokes, and lacunar infarcts will correlate with cognitive function (memory and executive function).

$$H_0: \rho_{\text{MRI-NPtest}} = 0$$

$$H_a: \rho_{\text{MRI-NPtest}} \neq 0.$$

For this analysis, we will use Spearman correlations, Pearson correlations, and/or multiple regression.

The 3rd secondary hypothesis involves comparing the ability of regular MRI and VMRI to predict neurocognitive injury. The 3rd secondary hypothesis is:

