Cortical gray matter and hippocampal volume will demonstrate a more significant correlation with executive and memory cognitive functions than the correlation of WML or lacunar infarcts with these same cognitive functions.

The statistical analysis will not involve a formal hypothesis test, but in statistical terms the hypothesis can be written as:

$$H_0: \rho_{\text{MRI-Nptest-Vol}} - \rho_{\text{MRI-Nptest-Reg}} = 0$$

$$H_a: \rho_{\text{MRI-Nptest-Vol}} - \rho_{\text{MRI-Nptest-Reg}} \neq 0.$$

For this analysis, we will descriptively compare Spearman or Pearson correlations.

The last secondary hypothesis involves randomizing 36 people who had a baseline WAIS-III PIQ score  $\leq 90$  to two treatment groups. We will treat one group with transfusion for 6 months and the other group with standard care for six months. After the six months of treatment we will perform a before and after comparison of the WAIS-III PIQ results, using within subject WAIS-III PIQ change scores as the outcome. We expect that on average patients who receive transfusion will show at least a five-point improvement when retested after six months of transfusion. Although this secondary hypothesis expresses the expected direction of effect independently of the observed affect in the control group, the statistical analysis will follow common practice and first use a 2-sided hypothesis test with an alpha of 0.05 to compare the mean within subject WAIS-III PIQ change score in the two groups. Second, we will calculate a 95% CI for the true effect of transfusion on WAIS-III PIQ within subject change scores for the group who received transfusion. We will use either a t-test, a Wilcoxon Two-Sample test, or a regression model to test the hypothesis. For statistical analysis we can express this secondary hypothesis as the mean within subject change score in WAIS III PIQ for the transfusion group will be different than the mean within subject change score in the control group:

$$H_0: \mu_{\text{diff, trt}} - \mu_{\text{diff, control}} = 0.$$

$$H_a: \mu_{\text{diff, trt}} - \mu_{\text{diff, control}} \neq 0.$$

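### The analyses in Section 13.2 do not estimate what secondary hypotheses 2 and 3 state: a comparison of proportions becomes a set of correlations, and the normal-MRI subgroup is not analysed

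*Protocol*

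**What the plan says.** **Hypothesis 2.** Protocol Section 6.2 reads: "A larger percentage of adult patients with abnormal MRIs will have abnormal NP testing than those with normal MRIs". Section 13.2 repeats this for SCD patients: "patients with SCD and abnormal MRIs will have a higher proportion of abnormal NP test results than the patients with SCD and normal MRIs". It then re-expresses the hypothesis for analysis as H0: rho = 0. The MRI side is cortical gray matter volume, hippocampal volume, white matter lesions (WML), cortical strokes and lacunar infarcts; the other side is memory and executive function. On method: "we will use Spearman correlations, Pearson correlations, and/or multiple regression". No covariates are named, and no comparison of two proportions is planned. The test is two-sided at 0.05. The synopsis (Section 1) says that only the primary hypothesis will be tested and that the secondary hypotheses are matters of estimation.

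**Hypothesis 3.** Section 6.2 reads: "Volumetric MRI will detect brain dysfunction in patients with abnormal neurocognitive tests but normal qualitative MRI". Section 13.2 describes it instead as a contest between regular and volumetric MRI in predicting neurocognitive injury: "Cortical gray matter and hippocampal volume will demonstrate a more significant correlation with executive and memory cognitive functions", compared with WML or lacunar infarcts. There is no formal test. Spearman or Pearson correlations are compared descriptively, and no restriction to patients with normal MRI is stated.

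**Head size.** Total intracranial volume (ICV) is among the volumetric results to be delivered (end of Section 10.2.3), but Section 13.2 does not use it.

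**The concern.** A hypothesis about the percentage of abnormal patients in two MRI groups is answered by a difference in proportions. A hypothesis about patients who look normal on qualitative MRI is answered only within those patients. Section 13.2 provides neither. It never applies the normal/abnormal split of MRI or NP in an analysis, although both hypotheses are built on that split.

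At stake is the interpretation of two of the four secondary hypotheses. A report that follows the text could give a non-zero correlation and present it as support for hypothesis 2. It could give a volume correlation driven by patients with visible lesions and present it as support for hypothesis 3. In the second case an unadjusted volume correlation could also reflect head size, or age across the 21-55 range, rather than disease.

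**Working it through.** The protocol gives no sample size, power or precision for hypotheses 2 or 3, so there is no figure of its own to reproduce for them. The only sample size involved is the 120 patients from the primary hypothesis, and that does reproduce. Section 13.1's formula with SD 15, difference 8, two-sided 0.05, 80% power and k = 0.3 gives m = 55.19, n1 = 55.19 x 1.3/0.6 = 119.6 and n2 = 0.3 x 119.6 = 35.9, that is 120 and 36.

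**1. Does rho different from 0 imply a difference in proportions?** Take a volume and an NP score, both standard normal, with correlation 0.30. Call NP abnormal if it lies more than 1 SD below the mean. Let MRI status be unrelated to both. The abnormal-NP proportion is then the same in both MRI groups. A simulation of 2,000,000 draws gave rho = 0.30 with 15.8% abnormal NP in each group. Rejecting rho = 0 therefore does not establish hypothesis 2. This is a deliberately clean case for the volume measures. WML and infarcts help to make a scan abnormal, so their correlations lie closer to the hypothesis, but they still do not estimate a difference in proportions.

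**2. Does a pooled correlation speak to the normal-MRI group?** Suppose half the patients have an abnormal MRI, with a volume-NP correlation of 0.50 in them and 0 in normal-MRI patients, and equal means and variances. The pooled correlation is 0.5 x 0.50 + 0.5 x 0 = 0.25. The simulation gave 0.25 pooled and 0.00 in the normal-MRI group. In addition, WML and lacunar infarcts should be few or absent where the qualitative MRI is normal, so the planned volume-versus-lesion comparison draws mainly on patients outside the target group.

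**3. Is the comparison in hypothesis 2 feasible?** The share with abnormal MRI is an assumption, shown over a range. With 0.5 as the worst-case proportion in each group, the half-width is 1.96 x sqrt(0.25/n_abn + 0.25/n_norm):

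| Abnormal MRI | n abnormal / normal | Half-width |
|---|---|---|
| 20% | 24 / 96 | 1.96 x sqrt(0.01302) = 0.224 |
| 30% | 36 / 84 | 1.96 x sqrt(0.00992) = 0.195 |
| 50% | 60 / 60 | 1.96 x sqrt(0.00833) = 0.179 |

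These figures are unadjusted.

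**4. How large is the hypothesis 3 target group?** If 50% to 80% have a normal MRI and 30% to 50% of those have abnormal NP (assumptions), the group runs from 120 x 0.5 x 0.3 = 18 to 120 x 0.8 x 0.5 = 48 patients.

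**5. Testing versus estimation.** The synopsis and Section 13.2 cannot both stand for hypothesis 2. If the tests were run on five MRI measures by two domains, that is 10 tests at 0.05. The chance of at least one false positive would be 1 - 0.95^10 = 0.40 if they were independent.

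**The case against.** The strongest reply is that the secondary objective in the synopsis is only to determine the association between neurocognitive dysfunction and imaging abnormalities, and correlations do address that. The analyses are secondary, the one for hypothesis 3 is openly descriptive, and covariates and ICV scaling are commonly left to a statistical analysis plan. Much of this stands. It bears on how serious the point is, and it makes rewording the hypotheses a legitimate remedy. It does not remove the contradiction, because Section 13.2 itself restates the comparison of proportions and then replaces it.

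A reader might infer more than the protocol supports:

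- *That both analyses are unadjusted.* For hypothesis 2 multiple regression is allowed, so adjustment there is optional and unspecified. Only for hypothesis 3 are simple correlations the sole method listed.
- *That hypothesis 2 uses brain volumes alone.* Its list includes WML, cortical strokes and lacunar infarcts.
- *That hypothesis 3 will rank correlations by p-value.* The reference to a more significant correlation is loose wording. The plan compares rho descriptively, without a test.
- *That scanner differences are uncontrolled.* Section 8.1 speaks of about eight sites and gives no scanner count. Sections 10.2.2 and 12.3 require a standardized imaging protocol, phantom scans and a volunteer re-scan.
- *That half the patients will have an abnormal MRI.* The pilot figure of 14 of 28 (Section 5.3.3) comes from patients evaluated for new non-focal symptoms, hence the range above.

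**Conclusion.** The point holds as a mismatch inside the protocol. Followed as written, Section 13.2 would yield neither the difference in proportions in hypothesis 2 nor any result specific to the normal-MRI patients in hypothesis 3. It also contradicts the synopsis on whether hypothesis 2 is tested. The size of any wrong conclusion cannot be computed from the protocol; the examples show only that the planned and stated quantities can part completely. The comparison in hypothesis 2 could be estimated to within roughly 18 to 22 points, given 120 patients with both assessments and 20% to 50% abnormal MRI. Precision for hypothesis 3 will be limited.

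This should be fixed, but it is not critical. A reader might infer that it undermines the trial's main result. It does not: the primary comparison, its sample size and the Phase II randomization do not depend on these analyses.

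**What to change.** Amend Section 13.2, or settle the following in the analysis plan before MRI and NP results are analysed together:

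- **Hypothesis 2.** Estimate the difference in the proportion with abnormal NP between abnormal-MRI and normal-MRI SCD patients, with a 95% CI. Pre-specify a norm-based cut-off on the memory and executive tests. PIQ can supplement this, but the threshold of 90 or below is a Phase II entry criterion, not a definition of abnormal memory or executive function. Add an estimate adjusted for age, sex, education and site. If a logistic model is used, report a standardised risk difference, since the model alone gives odds ratios.
- **Hypothesis 3.** Among SCD patients with normal qualitative MRI, compare ICV-adjusted gray-matter and hippocampal volumes between those with abnormal and those with normal NP, adjusting for age, sex and education. Regressing NP score on those volumes in the same patients is an acceptable alternative.
- **Correlations and testing.** Keep the planned correlations as exploratory estimates, and bring the 0.05 test of hypothesis 2 into line with the estimation-only statement in the synopsis.

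The alternative is to reword hypotheses 2 and 3 as the correlation questions that Section 13.2 analyses.

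The cost is revised wording and a few more models on data the protocol already collects. The downside is wide intervals in the normal-MRI subgroup, which the report should state.

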#### **5.2.5 SECONDARY HYPOTHESIS 4**

*Correction of anemia with transfusion therapy will improve the cognitive function in SCD patients with abnormal neurocognitive testing more than standard care.*

We propose that a group of patients with NP abnormalities who undergo a transfusion regimen of six months duration will show more improvement in neurocognitive function than a group of patients with NP abnormalities who receive standard care. After baseline NP and MRI testing, we will randomize 36 patients to a six-month transfusion protocol or standard care alone, and then retest them on the NP battery. We expect that patients with baseline WAIS III PIQ scores  $\leq 90$ , will show improvement when retested after six months of transfusion that is on average five points more than any average within subject improvement observed in a group of patients that receives standard care alone. We expect patients in the standard care group to have on average no improvement in WAIS-III PIQ scores after six months of standard care.

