## 7 STUDY DESIGN

### 7.1 DESCRIPTION OF PRIMARY AND SECONDARY ENDPOINTS

The primary endpoint is completion of baseline WAIS III-PIQ studies in 120 subjects and 36 controls. Assuming a 20% attrition rate, 150 subjects and 45 controls will be recruited.

Secondary endpoints include completion of the entire baseline NP battery and MRI studies in 120 subjects and 36 controls. After consent and randomization, the final secondary endpoint is completion of the transfusion protocol and demonstration of at least an average five-point within-subject improvement in WAIS-PIQ above any average within-subject improvement observed in the standard care group, total number of patients is 30 (15 in each group). Thirty-six patients meeting these criteria will be randomized, assuming 80% completion. Randomization in the transfusion phase of the study is appropriate in order to discriminate, as much as possible, intervention effects from re-test effects.

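### Section 13.2 labels a before-after interval from the transfused arm alone as the effect of transfusion, so regression to the mean and re-test gain are counted as treatment effect

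*Protocol*

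**What the plan says.** Protocol section 13.2 sets out two steps for the transfusion hypothesis. The plan will "first use a 2-sided hypothesis test with an alpha of 0.05 to compare the mean within subject WAIS-III PIQ change score" between the two groups. It will then "calculate a 95% CI for the true effect of transfusion on WAIS-III PIQ within subject change scores for the group who received transfusion". The section names no interval for the difference between arms. The same paragraph expects transfused patients to "show at least a five-point improvement when retested after six months of transfusion", and concedes that this "expresses the expected direction of effect independently of the observed affect in the control group".

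Elsewhere the effect is defined against the control arm. Section 7.1 sets the 5-point target "above any average within-subject improvement observed in the standard care group" and explains the design thus: "Randomization in the transfusion phase of the study is appropriate in order to discriminate, as much as possible, intervention effects from re-test effects". Section 5.2.5 likewise compares with standard care, and adds: "We expect patients in the standard care group to have on average no improvement in WAIS-III PIQ scores after six months of standard care". Section 9.4 says that mean changes will be compared between the groups.

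The synopsis limits formal hypothesis testing to the primary hypothesis and treats every secondary hypothesis, this one included, as a matter of estimation.

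**The concern.** A single-arm change estimates the transfusion effect plus whatever would have happened anyway. Here two upward components are foreseeable. First, patients are selected for a low value of the outcome itself (PIQ of 90 or less), so their mean is expected to move back up on retest. Second, they take the same test again, and section 7.1 itself cites re-test effects as the reason to randomise. The within-arm interval equals the transfusion effect only if standard care changes by exactly zero on average. Section 5.2.5 expects that, but the selection rule works against it.

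The interval matters because the synopsis makes estimation the aim for this hypothesis, and section 13.1 gives the between-arm test only 22% power for 5 points. A non-significant comparison beside a favourable interval labelled as the true effect of transfusion is therefore a realistic result, and the label invites the wrong reading.

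**Working it through.** **Inputs from the protocol.** SCD mean 85 (stated as 85 or less) and SD 15 (section 13.1); selection at PIQ ≤ 90 (sections 9.2 and 13.2); correlation between repeated scores 0.70 or 0.80, and 15 completers per arm (section 13.1).

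**1. The plan's own power figures.** Change SD = √(2 × 15² × (1 − ρ)); SE of the between-arm difference = change SD × √(2/15).

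| ρ | Difference | Change SD | SE | Power | Stated |
|---|---|---|---|---|---|
| 0.70 | 5 | 11.62 | 4.24 | 21.8% | 22% |
| 0.80 | 10 | 9.49 | 3.46 | 82.3% | 82% |

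Both reproduce, so the inputs are read as the plan intends.

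**2. Regression to the mean.** Treat the two scores as bivariate normal with equal means and SDs, and take the qualifying score as baseline. With a = (90 − 85)/15 = 0.333, λ = φ(a)/Φ(a) = 0.3774/0.6306 = 0.598.

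- Expected baseline among those selected: 85 − 15 × 0.598 = 76.0.
- Expected change with no treatment effect and no practice gain, (1 − ρ) × 15 × λ: 0.30 × 8.98 = 2.69 at ρ = 0.70; 0.20 × 8.98 = 1.80 at ρ = 0.80.
- As a share of the 5-point target: 54% and 36%.

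A simulation at ρ = 0.70 gave a mean change of 2.69 and a mean baseline of 76.04.

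Sensitivity, for ρ 0.70 to 0.80 and SD 15 to 20: means of 80 to 85 give 1.3 to 3.9 points; allowing a mean of 90 raises the top to 4.8.

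**3. How often the within-arm interval would exclude zero with no transfusion effect.** Among selected patients the baseline variance is 99.5, so change SD = √((1 − ρ)² × 99.5 + 15² × (1 − ρ²)). The chance that the lower 95% limit exceeds zero comes from the noncentral t with 14 df and noncentrality = expected change / SE. Nominal is 2.5%.

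| | ρ = 0.70 | ρ = 0.80 |
|---|---|---|
| Change SD | 11.12 | 9.22 |
| SE (n = 15) | 2.87 | 2.38 |
| Half-width | 6.2 | 5.1 |
| Regression alone | 13.9% | 10.5% |
| Plus practice gain of 2 points | 33% | 32% |
| Plus 4 points | 58% | 62% |
| Plus 6 points | 80% | 86% |

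The protocol gives no practice gain for this test, so the last three rows are assumptions that show sensitivity only.

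**4. Between-arm interval.** Regression and practice gain have the same expectation in both randomised arms and cancel. The half-width is t(28 df) × change SD × √(2/15): 8.3 points at ρ = 0.70 and 6.9 at ρ = 0.80. With the unselected change SDs of step 1 it is 8.7 and 7.1.

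**The case against.** The strongest reply is that the inferential analysis is already right. The between-arm test comes first, the stated hypotheses and power calculation concern the between-arm contrast, and no success decision hangs on the within-arm interval. A t-test or regression model also yields a between-arm interval as a matter of course, and an SAP may name it. The clause about the control group is concessive and leads straight into the between-arm test. This is also the fourth secondary hypothesis, studied in a pilot. All of that is fair, and it confines the fault to the interval and its label. It does not remove the fault: the protocol does not merely leave out a between-arm interval, it assigns the name of the treatment effect to a different quantity.

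On size, several points stand:

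- The larger percentages depend on assumed practice gains. The only untreated retest figure in the protocol is a 0.3-point gain on the WAIS-R in the controlled study cited in section 5.2.5, from renal patients. Adding 0.3 gives 16% at correlation 0.70 and 13% at 0.80.
- The 4.8-point upper bound needs a mean of 90, above the 85 or less that section 13.1 predicts.
- Patients 6 to 12 months past Phase I must score 90 or less a second time (section 10.5). Simulating that double qualification lowers the regression component to about 1.9 points at correlation 0.70 and 1.1 to 1.2 at 0.80.

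These shrink the bias but do not change its direction.

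**Conclusion.** The concern holds. As written, section 13.2 estimates before-after change in one arm and calls it the effect of transfusion, contrary to sections 5.2.5 and 7.1. Under the protocol's inputs the estimate is biased in favour of transfusion by an expected 2.7 points (correlation 0.70) or 1.8 points (0.80) before any practice gain. The interval then excludes zero four to six times as often as it should when transfusion does nothing (10.5% to 13.9% against 2.5%). This rests on normal scores, SD 15 as the unselected SD, and the qualifying score serving as baseline. The between-arm test, the Phase I primary analysis and the sample size are not affected.

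**What to change.** Replace the interval sentence in section 13.2 with wording such as: *We will report the between-arm difference in six-month WAIS-III PIQ (transfusion minus standard care, adjusted for baseline PIQ) with its 95% CI as the estimate of the transfusion effect; within-arm changes will be presented descriptively.* The difference in mean change scores would serve equally well against this bias; adjusting for baseline is a choice made for precision. In the same paragraph, restate the 5-point expectation as a gain over standard care, so that it agrees with section 7.1.

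No new data, visits or patients are needed. The cost is a wider interval: about ±8.3 instead of ±6.2 points at correlation 0.70, and about ±6.9 instead of ±5.1 at 0.80, using the change SDs under selection and no gain from baseline adjustment. That width is an honest statement of what 15 patients per arm can show.
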